5.2.2.2. Ratio of fold increase analysis

Fold increase of RSVPreF3 IgG-specific antibody concentrations over fold increase of RSV-A neutralizing antibody titers (ratio of fold increase post- over pre-vaccination) will be tabulated using descriptive statistics. This analysis will include calculation on:

- Geometric mean ratios with corresponding 95% CIs of RSVPreF3 IgG-specific antibody concentration over RSV-A neutralizing antibody titers at pre-vaccination for each group and
- Geometric mean ratios with corresponding 95% CIs of fold increase post/pre (Day 31, Delivery and Day 43 post-delivery/Day 1) between RSVPreF3 IgG-specific antibody concentration and RSV-A neutralizing antibody titers for each group.

Similar analysis will be performed between RSVPreF3 IgG-specific antibody concentrations and RSV-B neutralizing antibody titers.

5.2.2.3. Between group analysis

This analysis is exploratory.

For the analysis of maternal subjects at each time point (Day 31, Delivery, and Day 43 post-delivery), the model will be explored and fitted via the proc mixed procedure according to the following code:

```
PROC MIXED data=sero;
  CLASS /*subjid*/ group ges_age_cat age_cat center;
  MODEL log_val = baseline group ges_age_cat age_cat
inter_vac_del center /ddfm=kenwardroger outp = pred;
  /*RANDOM Subjid*/;
  LSMEANS group/pdiff cl alpha=0.05;
RUN;
```

where log_val represents the log-transformed antibody value of the immunogenicity variable at a given post baseline timepoint, group indicates the study group, ges_age_cat is the gestational age category at vaccination ($28^{0/7}$ - $31^{0/7}$, $31^{1/7}$ - $33^{6/7}$ weeks), age_cat is the age category at vaccination (18 – <35 years and \geq 35 years), inter_vac_del is the interval between vaccination and delivery (days). The inclusion of age category at vaccination, interval between vaccination and delivery, and center in the model depends on the availability of the variable (inter_val_del may not be available at Day 31 analysis) and the necessity, therefore, the above SAS code serves as a reference and may be adjusted according to the analysis needs.

CONFIDENTIAL209544 (RSV MAT-004)
Statistical Analysis Plan Amendment 3

For the analysis of infants at each time point (cord blood at Delivery, Day 43 post-birth, Day 121 post-birth, and Day 181 post-birth), similar model will be explored:

```
PROC MIXED data=sero;
  CLASS /*subjid*/ group center ges_age_cat ges_age_birth;
  MODEL log_val = baseline group ges_age_cat /*inter_vac_del*/
  ges_age_birth center /ddfm=kenwardroger outp = pred;
  /*RANDOM Subjid*/;
  LSMEANS group/pdiff cl alpha=0.05;
  RUN;
```

Baseline is pre-vaccination logarithm10 transformation of the concentrations/titers from maternal subjects, ges_age_birth is gestational age category at birth (> 37 weeks; ≤ 37 weeks) for infants. With the inclusion of gestational age category at vaccination (ges_age_cat) in the model, this categorical variable ges_age_birth provides similar information as continuous variable inter_vac_del, therefore the inclusion of either variable in the model could be adjusted according to the analysis needs.

The ratio of GMTs/GMCs between vaccine groups and the corresponding 95% CI will then be constructed by exponentiating the mean difference and its confidence interval between vaccine groups on the logarithm10 scale estimated from the model. Summary tables will show adjusted GMT/GMC for vaccine groups, and ratios of GMTs/GMCs between vaccine groups along with the 95% CI.

If deemed necessary, an analysis of variance model for repeated measures will be fitted to assess the mean profile in each group over time for both maternal and infant subjects separately. Below is the sample SAS code for the analysis of maternal subjects, and similar codes could be explored for the analysis of infants.

```
PROC MIXED data=sero;
  CLASS subjid group visit age_cat center ges_age_cat;
  MODEL log_val = baseline group | visit age_cat ges_age_cat
  inter_vac_del center/ddfm=kenwardroger outp = pred;
  RANDOM subjid;
  /*REPEATED visit/subject=subjid(group) type=un;*/
  LSMEANS group*visit/pdiff cl alpha=0.05;
  RUN;
```

Summary tables will present adjusted GMT/GMC with 95% CI for each group at each timepoint.

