3. STUDY DESIGN

Figure 1 and Figure 2 provide overviews of the study design for maternal and infant subjects, respectively.

Figure 1 Overall design – maternal subjects

H/B= hematology/biochemistry, Hct- hematocrit, I= humoral immune response

If Screening blood sample collected \leq 15 days before Visit 1, hematology/biochemistry not required at Visit 1

[figure not shown]
Subjects will be vaccinated year-round and will not be limited to seasonal enrolment

*Pregnancy-related AESIs identified after Day 43 will continue to be reported as such.

CONFIDENTIAL

209544 (RSV MAT-004)
Statistical Analysis Plan Amendment 3

Figure 2 Overall design– infant subjects

NB = Newborn; I=humoral immune response: infants will be randomized 1:1:1 to one of the 3 subcohorts shown.

*Blood sample to be collected within 3 days after birth **ONLY** if a cord blood sample is not collected

**Neonatal AESIs identified after Day 43 (e.g., congenital anomalies) will continue to be reported as such.

***Infant subjects' parent(s)/LAR(s) will be contacted at least monthly to ensure RTI eDiary compliance.

Safety and disease surveillance data collected *after* Visit 4-NB will be reported in the database *in Epoch 003*.

- Study Type: self-contained.
- Experimental design: Phase II, observer-blind, randomised, placebo controlled, multi-centric, multi-country study with 3 parallel groups.
- Study Duration: Approximately 9 months (including the screening visit) for participating pregnant women; approximately 1 year after birth for participating infants.
- Control: Placebo.
- Epochs 001, 002 and 003 begin and end as described in [Table 2](#).
- Blinding is as described in [Table 2](#).
- Randomized intervention allocation: **Up to** 300 eligible pregnant women will be randomly assigned to 3 study (intervention) groups in a 1:1:1 ratio and at the same time, their (as yet unborn) infants will be randomly assigned to 3 blood sampling subcohorts (also in a 1:1:1 ratio) using an automated internet based system (SBIR). The system's randomisation algorithm will use a minimisation procedure accounting for maternal age at the time of vaccination (≥ 18 and < 35 years of age or ≥ 35 years of age), gestational age at the time of vaccination ($28^{0/7}$ - $31^{0/7}$; $31^{1/7}$ - $33^{6/7}$) and center. Minimisation factors will have equal weight in the minimisation algorithm.
- Study (intervention) groups are described in [Table 2](#)

CONFIDENTIAL

209544 (RSV MAT-004)

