The natural decay of antibody level will be determined using linear regression between the logarithm transformed antibody level (Y) and time t (age in days) with subject as a random effect. All infants have RSV neutralizing antibodies measured at birth (cord blood) or within 3 days after birth, and each infant in PPS sub-cohort will have blood sampling for RSV neutralizing antibodies at one of the following time points: Day 43 post-birth, Day 121 post-birth or Day 181 post-birth. Therefore, in the natural decay model, each infant will have maximum 2 RSV neutralizing antibodies measures, one at birth or within 3 days after birth and the other at Day 43 post-birth, Day 121 post-birth or Day 181 post-birth depending on the sub-cohorts where the infants are.

The following SAS code will be explored:

```
PROC MIXED DATA=<filename>;
  CLASS PID;
  MODEL LOG_Y = t /s outp=pred;
  RANDOM Int t / sub=PID type=UN G GCORR;
RUN;
```

The choice of correlation structure and other parameters may be further adjusted according to the data and analysis needs.

The predicted value will be computed using the following formula

$$A_t = A_0 \exp(-K_e t)$$

where, A_t and A_0 are antibody titres at times t and zero, respectively, K_e is the constant rate of antibody change with time, defined as the estimate of model.

CONFIDENTIAL209544 (RSV MAT-004)
Statistical Analysis Plan Amendment 3

In addition, the half-life ($t_{1/2}$) of antibody (i.e. the time required for titre to decrease by one-half) will be displayed using the following equations of declining antibody titre:

$$\text{when } A_t = \frac{1}{2} A_0$$

$$t_{1/2} = 0.693 / K_e$$

A summary table will be prepared to show the number of infants included in the model, the model estimate of the antibody decay rate, and the half-life of the antibody.

In case cord blood samples are missing in 20% or more of infants in a single study group, separate analysis for infants with cord blood and infants with a blood sample within 3 days after birth will be performed.

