9.1.2. Immunogenicity

For a given subject and given immunogenicity measurement, missing or non-evaluable measurements will not be replaced. Therefore, an analysis will exclude subjects with missing or non-evaluable measurements.

- For the within-group assessment, the descriptive analysis performed for each assay at each timepoint will exclude subjects with a missing or non-evaluable measurement.
- For the between group assessments, statistical model will be fitted based on the subjects having a result at both the baseline and the considered timepoint.

The GMT/GMC and its 95% CI will be obtained by exponentiating the mean and its 95% CI of the log-transformed titres/concentrations. All CI computed will be two-sided 95% CI.

Placental transfer is defined as the ratio of RSVPreF3 IgG-specific antibody concentrations between cord blood (or blood sample from infants collected within 3 days after birth if cord blood is not available) and maternal blood sample at delivery (or within 3 days after delivery if blood sample is not collected during delivery).

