IEC	Independent Ethics Committee
IM	Intramuscular
IRB	Institutional Review Board
IU/mL	International units per milliliter
LL	Lower Limit of the confidence interval
LLOQ	Lower Limit of Quantification
LRTI	Lower Respiratory Tract Illness
MAE	Medically attended adverse event
MedDRA	Medical Dictionary for Regulatory Activities
NA	Not Applicable
NB	Newborn
PD	Protocol Deviation
PPS	Per-Protocol Set
RTI	Respiratory Tract Illness
SAE	Serious Adverse Event
SAP	Statistical Analysis Plan
SBIR	GSK Biological's Internet Randomisation System

CONFIDENTIAL209544 (RSV MAT-004)
Statistical Analysis Plan Amendment 2

SD	Standard Deviation
SDTM	Study Data Tabulation Model
SPM	Study Procedures Manual
SR	Study Report
SRT	Safety Review Team
SUSAR	Suspected Unexpected Serious Adverse Reaction
TFL	Tables Figures and Listings
TOC	Table of Content
UL	Upper Limit of the confidence interval
ULOQ	Upper Limit of Quantification

CONFIDENTIAL209544 (RSV MAT-004)
Statistical Analysis Plan Amendment 2**1. DOCUMENT HISTORY**

Date	Description	Protocol Version
29 OCT 2019	first version	Final: 09 JUL 2019
10 MAR 2020	Amendment 1	Amendment 1: 27 JAN 2020
29 MAY 2020	Amendment 2	Amendment 2: 19 MAY 2020

Table below lists main changes in the SAP amendment 2 and their rationale

Section # and Name	Description of Change	Brief Rationale
Globally	Total number of maternal subjects / total number of infant subjects have each been changed to “up to 300.” Total number of maternal subjects per group / total number of infant subjects per group have each been changed to “up to 100.” Total number of infant subjects per blood sampling subcohort has been changed to “up to 33.”	213 subjects were vaccinated and subsequent enrollment was halted due to COVID-19.
Section 3, Study Design, Figure 1	References to Gestational age have been removed at Visits 2, 3 and 4.	The gestational age range at each of these visits was provided as a guide only. It has created confusion, since the provided gestational age interval does not perfectly line up with the preferred visit day or allowed interval for the corresponding visits. Therefore the gestational age ranges previously provided have been removed.

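### The infant dose comparisons at Day 43, 121 and 181 leave the paired birth titres unused; a joint birth-plus-follow-up model would give narrower intervals from the same data

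*SAP*

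**What the plan says.** **Design.** Under Study Design (section 3), the as yet unborn "infants will be randomly assigned to 3 blood sampling subcohorts (also in a 1:1:1 ratio". The three subcohorts are bled at Day 43, Day 121 or Day 181. All infants are to be sampled at birth, from cord blood or within 3 days. Section 5.2.2.4 draws the consequence: "each infant will have maximum 2 RSV neutralizing antibodies measures, one at birth or within 3 days after birth", the other at the age of the assigned subcohort.

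**Numbers.** Table 2 gives up to 100 mothers per group and up to 33 infants per subcohort within a group. The document history of SAP Amendment 2 records that "213 subjects were vaccinated and subsequent enrollment was halted due to COVID-19".

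**Infant comparison.** Section 5.2.2.3 fits a separate model at birth and at each of the three follow-up ages: "For the analysis of infants at each time point (cord blood at Delivery, Day 43 post-birth, Day 121 post-birth, and Day 181 post-birth". The code begins "MODEL log_val = baseline group ges_age_cat /*inter_vac_del" and goes on to gestational age at birth and center; the subject effect is commented out. The baseline term belongs to the mother: "Baseline is pre-vaccination logarithm10 transformation of the concentrations/titers from maternal subjects". Section 9.1.2 fixes who enters each between-group fit: "statistical model will be fitted based on the subjects having a result at both the baseline and the considered timepoint". The GMT/GMC ratios and their confidence intervals come from these fits.

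**Optional joint model.** The same section adds: "If deemed necessary, an analysis of variance model for repeated measures will be fitted to assess the mean profile in each group over time". This covers mothers and infants separately. Sample code is given for mothers only, and the described table shows adjusted GMT/GMC per group and timepoint.

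**The concern.** The sampling scheme is a planned-missing design. A correlated early value is intended for every infant, and chance decides which later age is observed. Such a design lets the birth values of infants not bled at a given age sharpen the comparison at that age. The per-age fits do not use this. At Day 43, 121 or 181 no birth value enters the model, neither from the infants bled then nor from the other two thirds.

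These are the dose comparisons with the smallest samples in the SAP, and they appear under the secondary infant immunogenicity endpoints in section 5.2.1. What is at stake is the width of their confidence intervals.

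**Working it through.** **Inputs from the SAP.** Allocation is 1:1:1 to arm and 1:1:1 to subcohort. 300/3 = 100 per arm and 100/3 = 33.3, which reproduces the 33 in Table 2. At 213 vaccinated, 213/3 = 71 per arm and 213/9 = 23.7, about 24 per arm per age. No exclusions or losses are deducted.

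**Inputs assumed.** rho is the correlation between log10 birth value and log10 follow-up value given the covariates, taken as equal across arms. The log10 SD is 0.4 for the interval example. The SAP states neither.

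**Formula.** Let n infants per arm have the follow-up value and N have the birth value. The variance of the arm mean at follow-up is

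- per-age fit: sigma²/n
- joint fit: sigma²[(1 - rho²)/n + rho²/N]

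The ratio of variances is 1 - rho²(1 - n/N), or 1 - (2/3)rho² at n/N = 1/3. The ratio of standard errors is its square root and does not depend on the SD. The effective number of infants per arm is n divided by the variance ratio.

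**Results at n/N = 1/3.**

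| rho | variance ratio | SE ratio, joint/per-age | per-age CI wider by (log scale) | effective n from 33 | effective n from 24 |
|---|---|---|---|---|---|
| 0 | 1.00 | 1.00 | 0% | 33 | 24 |
| 0.3 | 0.94 | 0.97 | 3% | 35 | 26 |
| 0.5 | 0.83 | 0.91 | 10% | 40 | 29 |
| 0.7 | 0.67 | 0.82 | 22% | 49 | 36 |
| 0.9 | 0.46 | 0.68 | 47% | 72 | 52 |

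**Interval example.** With SD 0.4 and 24 per arm, the SE of the log10 difference is 0.4 x sqrt(2/24) = 0.115. The 95% factor on the GMT ratio is 10^(1.96 x 0.115), or times/divided by 1.68, for the per-age fit. For the joint fit it is 1.61, 1.53 and 1.42 at rho 0.5, 0.7 and 0.9.

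**Simulation check.** Three arms, maternal baseline as covariate, 4,000 runs per setting, per-age ANCOVA against the bivariate maximum-likelihood estimate. For rho 0, 0.3, 0.5, 0.7 and 0.9 the SE ratios were:

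- 33 of 99 per arm: 1.00, 0.98, 0.91, 0.83, 0.69
- 24 of 71 per arm: 1.01, 0.97, 0.92, 0.81, 0.66

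Both agree with the formula, and neither estimator showed material bias.

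**Can the optional model stand in?** Three features of section 5.2.2.3 prevent it as written.

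- It states no condition that would trigger it, and infant code is only something that might be explored.
- Copying the maternal random subject intercept forces one covariance across birth, Day 43, Day 121 and Day 181.
- The commented-out unstructured matrix cannot be estimated over four infant visits, because no infant has two follow-up draws. A 2x2 matrix for birth plus one follow-up age can be.

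**The case against.** The strongest reply is that nothing here is wrong. A per-age ANCOVA on infants with a result is standard and unbiased. Section 5.2.2.3 labels the analysis exploratory, and section 6 calls all comparative analyses descriptive. The reference code may be adjusted, and a repeated-measures model is already allowed for. Its LSMEANS line requests pairwise differences with confidence limits, so the contrasts would be computed even though no ratio table is named. All of this stands, which is why the point concerns precision only.

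A reader might infer more, in three ways that the SAP does not support.

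- *That two thirds of the cord data are thrown away.* The SAP uses them in the cord comparison, in the placental transfer ratio and in the decay model of section 5.2.2.4. They are absent only from the follow-up comparisons.
- *That a high rho can be read off the 2-fold infection rule in section 5.2.2.4.* If 2-fold were two residual SDs (log10(2)/2 = 0.151) and the total SD were 0.3 to 0.5, then sqrt(1 - 0.151²/SD²) gives 0.87 to 0.95. The SAP does not tie the rule to any number of SDs. That section also first removes swab-positive infants and then trims high values, which section 5.2.2.3 does not do.
- *That statistical power is being lost.* No hypothesis, margin or power is stated for these comparisons, so only interval width is relevant.

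One further caution stands. Only subcohort assignment is random. Missed or out-of-window bleeds and per-protocol eliminations are not.

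**Conclusion.** This is a cheap improvement in precision, and the plan contains no error on this point. The planned ratios at Day 43, 121 and 181 are valid, but their intervals are wider than the sampling design allows whenever birth and follow-up values are correlated. The standard error could fall by about 3%, 9%, 18% or 32% at rho 0.3, 0.5, 0.7 or 0.9.

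The size rests on an assumed rho. The gain is small below about 0.4, and infection and differing decay may weaken the correlation by Day 181. The counts of 71 and 24 per arm are before exclusions; losses matter to the SE ratio only through n/N. The optional repeated-measures model does not close the gap as written.

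**What to change.** In section 5.2.2.3, prespecify for each of Day 43, Day 121 and Day 181 a two-outcome model:

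- Outcomes: log10 birth value in all infants, and log10 follow-up value in the subcohort bled at that age.
- Fixed effects: group by visit and covariate by visit, with center by visit only if the data support it.
- Covariance: `REPEATED visit / subject=subjid type=UN`, a 2x2 matrix.
- Report: the between-group GMT/GMC ratio with 95% CI at the follow-up visit.
- Sensitivity: the present single-age model.

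Amend section 9.1.2 so that infants with a birth value but no follow-up value may enter this model. Do not enter the cord value as a covariate. It is measured after vaccination, and conditioning on it would remove part of the vaccine effect being compared.

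The cost is some SAP wording and a few lines of code, with no new blood draw. The model assumes a linear birth/follow-up relation on the log scale. It also relies on missing at random for follow-up values lost for reasons other than subcohort assignment.

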	
 • The ratio between cord blood and maternal RSVPreF3 IgG-specific antibody concentrations 
All 3 endpoints measured on blood samples collected from maternal subjects at delivery and either cord blood, or (if cord blood cannot be collected) infant blood samples collected within 3 days after birth
	
 • Geometric mean of placental transfer will be tabulated with 95% CI by study group. • Percentage of infants with placental transfer ≥ 1 will be tabulated with exact 95 % CI by study group. 
Between group evaluation on vaccine formulations in terms of RSVPreF3 IgG-specific antibody concentrations / neutralizing antibody titers will be performed on cord blood at Delivery using a mixed effect model on the logarithm₁₀ transformation of the concentrations/titers, including the pre-vaccination logarithm₁₀ transformation of the concentrations/titers from maternal subjects, the vaccine groups, gestational age at vaccination, gestational age at birth (> 37 weeks; \leq 37 weeks), age category at vaccination, center and the interval between vaccination and delivery as covariates if appropriate.
 
In addition, if cord blood samples are missing in 20% or more of infants in a single study group, and if the data permit: RSV antibody concentrations/titers and persistence of RSV antibody concentrations/titers in infants through time will be evaluated separately in infants with cord blood samples and in infants from whom, instead, a blood sample was obtained within 3 days after birth.
 
The relationship between RSVPreF3 IgG-specific antibody concentration and RSV-A neutralizing antibody at delivery will be explored using scatter plots of individual values.

CONFIDENTIAL209544 (RSV MAT-004)
Statistical Analysis Plan Amendment 3

	Secondary Immunogenicity Endpoints	Statistical Analysis Methods

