Maternal subjects	
 • RSVPreF3 IgG-specific antibody concentration, and • Neutralizing antibody titers against RSV-A and • Neutralizing antibody titers against RSV B 
For RSV-A: Measured on the blood sample collected Day 43 post-delivery (Visit 6).
 
 • For RSV-B: Measured on blood samples collected from vaccinated maternal subjects at Day 1 before vaccination (Visit 1), Day 31 (Visit 3),, at Delivery (Visit 5) and at Day 43 post delivery (Visit 6). 	
For each assay, at each timepoint and by study group and age category (18 - <35 years ; ≥ 35 - years; overall):
 
 • Antibody titres/concentrations will be displayed using reverse cumulative curves. • GMTs/ GMCs will be tabulated with 95% CI and represented graphically. • Individual post-vaccination versus pre-vaccination results will be plotted using scatter plots. Results of the control group will be used as a reference. • Geometric mean of ratios of antibody titres/concentrations at each post-vaccination timepoint over pre-vaccination will be tabulated with 95% CI. • The distribution of antibody titres/concentration will be tabulated • Distribution of the fold increase of the antibody titres/concentrations (post- versus pre-vaccination) will be tabulated by pre-specified pre-vaccination titre category. 
Relationship between maternal RSVPreF3 IgG-specific antibody concentration and RSV-A neutralizing antibody, between RSV-A neutralizing antibody and RSV-B neutralizing antibody, and between RSV-B neutralizing antibody and RSVPreF3 IgG-specific antibody concentration at baseline, at day 31, at delivery and at day 43 post-delivery will be explored using scatter plots of individual values.
 
In addition, between group evaluation of vaccine formulations in terms of RSVPreF3 IgG-specific antibody concentrations and Neutralizing antibody titers against RSV-A and RSV-B will be performed at Day31, at Delivery and at Day 43 post-delivery using a mixed effect model on the logarithm₁₀ transformation of the concentrations/titers, and including the pre-vaccination logarithm₁₀ transformation of the concentrations/titers, the vaccine groups, gestational age at vaccination, and the interval between vaccination and delivery if available as covariates if needed.

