	
these 3 cohorts at the time of maternal randomization to intervention
 
For neutralizing antibody titers against RSV-B only: measured on the cord blood sample collected at delivery, or on a blood sample collected from the infant within 3 days after birth (if no cord blood sample can be obtained). (Note: RSV-A neutralizing antibody at birth is a primary immunogenicity objective).
	
including the pre-vaccination logarithm₁₀ transformation of the concentrations/titers from maternal subjects, the vaccine groups, gestational age at vaccination, gestational age at birth (> 37 weeks ; ≤ 37 weeks), and the interval between vaccination and delivery as covariates if appropriate and needed.
 
In addition, if cord blood samples are missing in 20% or more of infants in a single study group, and if the data permit: RSV antibody concentrations/titers and persistence of RSV antibody concentrations/titers in infants through time will be evaluated separately in infants with cord blood samples and in infants from whom, instead, a blood sample was obtained within 3 days after birth.
 
The relationship between RSVPreF3 IgG-specific antibody concentration and RSV-A neutralizing antibody, between RSV-A neutralizing antibody and RSV-B neutralizing antibody, and between RSV-B neutralizing antibody and RSVPreF3 IgG-specific antibody concentration at delivery will be explored using scatter plots of individual values.

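### The between-group models treat the minimisation factors inconsistently and include delivery-timing covariates that are determined after vaccination

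*SAP*

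**What the plan says.** All references are to SAP Amendment 3 unless stated.

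**Allocation (Section 3).** The "randomisation algorithm will use a minimisation procedure accounting for maternal age at the time of vaccination", together with gestational age at vaccination and center. "Minimisation factors will have equal weight in the minimisation algorithm".

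**Model text (5.2.1).** The primary maternal row and the primary cord-blood row each name all three factors. The cord-blood row also has gestational age at birth and ends with "age category at vaccination, center and the interval between vaccination and delivery as covariates if appropriate". The secondary maternal row covers the same IgG and RSV-A comparisons at Day 31 and Delivery, and adds RSV-B and Day 43 after delivery. It lists only "the vaccine groups, gestational age at vaccination, and the interval between vaccination and delivery if available as covariates if needed", besides the baseline titre. The secondary infant row also covers cord blood. It names gestational age at vaccination, gestational age at birth "and the interval between vaccination and delivery as covariates if appropriate and needed", again without age or center.

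**Model code (5.2.2.3).** The maternal code has "CLASS /*subjid*/ group ges_age_cat age_cat center" and an active interval-to-delivery term, and is meant for each time point including Day 31. The infant code has "CLASS /*subjid*/ group center ges_age_cat ges_age_birth", with the interval commented out. The SAP adds that age, interval and center in the maternal model depend on availability and need, that the interval may be missing at the Day 31 analysis, and that the infant model may use either delivery-timing variable. It labels the analysis exploratory.

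**The concern.** There are two separate issues.

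First, a factor used to balance allocation belongs in the model that compares the groups. Minimisation makes the groups alike on that factor, and an analysis that ignores it generally reports a standard error larger than it needs to be. Here the same comparison is also specified with different covariates in different places, so the adjusted ratio is not settled by the plan.

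Second, the interval to delivery and gestational age at birth are not baseline variables. The SAP lists preterm birth and the pathways leading to it as safety outcomes (Section 2), so it should not presume that delivery timing is untouched by allocation. If timing is affected, adjusting for it removes the part of the effect that runs through timing. It can also open a path through unmeasured causes that timing and antibody level share. At Day 31 the covariate is usually fixed only after the outcome has been measured.

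At stake is what the adjusted geometric mean ratio between groups means, for endpoints that include the primary immunogenicity ones.

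**Working it through.** The SAP gives no sample size calculation, SD or effect size for these models, so there is no stated figure to reproduce. The first check is a comparison of texts. The others use assumed inputs.

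**1. Covariates side by side**

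| Place | Maternal age | GA at vaccination | Center | Delivery timing |
|---|---|---|---|---|
| Section 3, minimisation | yes | yes | yes | not applicable |
| 5.2.1 primary, maternal | yes | yes | yes | interval |
| 5.2.1 primary, cord blood | yes | yes | yes | GA at birth, interval |
| 5.2.1 secondary, maternal | no | yes | no | interval |
| 5.2.1 secondary, infant and cord | no | yes | no | GA at birth, interval |
| 5.2.2.3 maternal code | yes | yes | yes | interval |
| 5.2.2.3 infant code | no | yes | yes | GA at birth; interval commented out |
| 5.2.2.3 repeated-measures code, maternal | yes | yes | yes | interval |

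Maternal IgG and RSV-A at Day 31 and Delivery therefore have two written covariate sets, and cord-blood IgG and RSV-A have three. This step needs no assumption.

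**2. Precision lost by leaving out maternal age.** For a balanced binary factor with prevalence p and effect β on the log10 scale, the standard error is inflated by √(1 + p(1−p)β²/SD²) − 1. The assumptions are SD 0.3 to 0.4 log10, 15% to 30% of women aged 35 or over, and β from 0.05 to 0.2.
- Smallest: √(1 + 0.15×0.85×0.05²/0.4²) − 1 = 0.10%.
- Largest with β = 0.1: √(1 + 0.3×0.7×0.1²/0.3²) − 1 = 1.16%.
- Largest overall: √(1 + 0.3×0.7×0.2²/0.3²) − 1 = 4.56%.

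The loss from leaving out center cannot be computed, because the SAP gives no between-center variance.

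**3. Timing at Day 31.** Vaccination falls between 28w0d and 33w6d (Section 3). Day 31 is 30 days later, or 4w2d, so the sample is nominally taken between 32w2d and 38w1d of gestation. For a term birth, delivery usually follows it. At the first analysis (7.1.1) about 75 women will have reached Day 31 and about 24 will have delivered, so roughly 75 − 24 = 51 would have no interval to enter.

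**4. Effect of adjusting for delivery timing.** If allocation shifts delivery by d days and log10 titre changes by s per day of interval, the interval-adjusted contrast misses s×d. For s = 0.01 and d = −3, 10^0.03 = 1.07. For s = 0.01 and d = −7, 10^0.07 = 1.17. A simulation used 2,000 runs, two arms of 71 (213/3, from the 213 vaccinated reported in the document history of SAP Amendment 2), residual SD 0.35 log10 and a direct group effect of 0.1 log10. It gave the following factors by which the estimated ratio departs from the total effect:

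| Slope per day | Shift, days | Baseline factors only | Plus interval | Plus binary GA at birth |
|---|---|---|---|---|
| 0.01 | 0 | 1.004 | 1.004 | 1.005 |
| 0.003 | 0 | 0.998 | 0.998 | 0.998 |
| 0.01 | −3 | 1.001 | 1.071 | 1.017 |
| 0.01 | −7 | 1.001 | 1.174 | 1.049 |
| 0.005 | −7 | 1.002 | 1.084 | 1.026 |
| 0.005, with an unmeasured common cause | −7 | 1.002 | 1.169 | 1.066 |

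The last column omits maternal age, as the infant code does. Center was not simulated. With no shift, adjusting for the interval caused no bias and lowered the standard error from 0.0613 to 0.0591 (about 3.6%) at 0.01 per day. At 0.003 per day it made no difference.

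**5. Scale.** The 95% half-width on a ratio is 10^(1.96×SD×√(2/n)). With n = 71 this is 1.26 to 1.35 fold for SD 0.3 to 0.4. With n = 23 (213/9 ≈ 23.7 per group and infant subcohort) it is 1.49 to 1.70 fold.

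**The case against.** The other side has real points. The analysis is labelled exploratory, and Section 6 makes all comparisons descriptive, so no error rate or decision rule depends on it. The covariates are conditional in every row, and the SAP describes the maternal code as a reference. GMTs and GMCs by group, without this adjustment, are tabulated anyway, and 5.2.2.1 tabulates cord-blood geometric means by interval. If groups differ in delivery timing only by chance, adjusting for it corrects an imbalance and may gain precision.

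Most of this stands and limits the size of the point. The conditional wording does not resolve it: it leaves the choice among conflicting covariate sets to the time of analysis. The Day 31 caveat concerns whether the interval is available, not whether it is a valid covariate there.

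A reader might infer something stronger: that the models in general discard the minimisation factors and put delivery timing in their place, losing precision and biasing the comparison. The documents do not support that. The maternal codes and both primary rows keep all three factors, the infant code lacks only age, and in the maternal code the interval is added to the factors. Nor do the documents show that vaccination shifts delivery. Preterm birth as a safety outcome is a reason not to assume the absence of an effect, not evidence of one. It would also go too far to call ratios from different rows incomparable because of the omitted factors: in a linear model on log titre, leaving out balanced baseline factors changes mainly the precision.

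**Conclusion.** The point holds as an inconsistency in the covariate sets plus an avoidable choice of post-vaccination covariates. The inconsistency is plain from the text. Its cost in precision is small for maternal age, about 0.1% to 5% of the standard error and under 1.2% if the age effect is 0.1 log10 or less. For center the cost is unknown.

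The delivery-timing covariates matter only if allocation affects delivery. For the comparison of the two doses, that means the doses would have to affect it differently. In that case the adjusted ratio departs from the total effect by about 1.07 to 1.17 with the interval, or 1.02 to 1.07 with binary gestational age at birth. These figures rest wholly on the assumed slopes and on shifts of 3 to 7 days, and they are smaller than the confidence half-widths above. The change is still worth making: it costs almost nothing and gives one defined estimate based on baseline variables.

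**What to change.** - Set one main covariate set for all assays and time points: log10 maternal baseline, group, age_cat, ges_age_cat and center.
- Add age_cat to the infant code, and add age category and center to the secondary maternal and infant rows of 5.2.1.
- Remove inter_vac_del from the Day 31 model.
- Report models with inter_vac_del or ges_age_birth as labelled supportive analyses at Delivery and later.

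This is an edit to wording and code and needs no new data. The downside is a possible small loss of precision in the main model where the interval predicts titre, which the supportive model would show. The change does not fully restore the randomised comparison for infants, because their Per Protocol set still excludes births less than 4 weeks after vaccination (4.1.2 and code 3100). The report should say so.
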